14.1 Sample Size Determination

The sample size chosen for this study was selected without statistical considerations. The sample size of 36 patients in total (18 per cohort with a ratio of 2:1 of active study drug:matching placebo) has been designed to meet the study safety, tolerability, and PD objectives.

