14.3 Statistical Analyses

Detailed methodology for summary and statistical analyses of the data collected in this study will be documented in a Statistical Analysis Plan (SAP). The SAP will be prepared by Celerion and agreed upon with the Sponsor. This document may modify the plans outlined in the protocol; however, any major modifications of the primary endpoints definition and/or its analysis will also be reflected in a protocol amendment. Additional statistical analyses other than those described in this section may be performed if deemed appropriate.

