14.3.1 Safety and Tolerability Analyses

All safety data will be populated in the individual CRFs. All safety data will be listed by patients.

The placebo patients from all cohorts will be pooled into a single placebo group for all summaries and presentations.

Dosing dates and times will be listed by patient.

Incidence and time of bleeding from the HD access sites on the AV fistula (or AV graft), as described in [Section 13.2.6](#), will be counted and recorded. Active treatment versus pre-treatment, placebo, and post-treatment results will be compared.

AEs will be coded using the most current version of Medical Dictionary for Regulatory Activities (MedDRA®) available at Celerion and summarized by treatment (2 active dose levels and pooled placebo) for the number of patients reporting the treatment emergent adverse event (TEAE) and the number of TEAEs reported. A by-patient AE data listing including verbatim term, coded term, treatment, severity, and relationship to study drug will be provided.

Safety data including ECGs, vital signs assessments, clinical laboratory results, and vascular access site reaction will be summarized by treatment (2 active dose levels and pooled placebo) and point of time of collection.

Descriptive statistics using appropriate summary statistics will be calculated for quantitative safety data as well as for the difference to baseline, when appropriate. In addition, a shift table describing out of normal range shifts will be provided for clinical laboratory results.

Concomitant medications will be listed by patient and treatment (2 active dose levels and pooled placebo) and coded using the most current version of the World Health Organization drug dictionary available at Celerion. Medical history will be listed by patient.

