7.10 Vascular Access Site Reaction

Vascular access site reaction will be assessed at predose and 4 hours post dose on Day 1 and at start and 20 minutes post HD on Day 3. Any new abnormal findings inconsistent with past skin injuries as expected in patient on chronic HD will be reported and summarized as AEs. All data collected on the CRF will be listed.

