8. SUMMARY OF CHANGES FROM PROTOCOL-PLANNED ANALYSIS

The analyses described in this SAP are aligned with those analyses described in the protocol.

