14.3.3 Narratives of Deaths, other Serious and Certain other Significant Adverse Events

14.3.4 Abnormal Laboratory Value Listing (each patient)

Table 14.3.4.1 Out-of-Range Values and Recheck Results – Serum Chemistry (Safety Population)

Table 14.3.4.2 Out-of-Range Values and Recheck Results – Hematology/Coagulation (Safety Population)

Table 14.3.4.3 Out-of-Range Values and Recheck Results – Urinalysis (Safety Population)

14.3.5 Displays of Other Laboratory, Vital Signs, Electrocardiogram, Physical Examination, and Other Safety Data

Table 14.3.5.1 Clinical Laboratory Summary and Change from Baseline – Serum Chemistry (Safety Population)

Table 14.3.5.2 Clinical Laboratory Shift from Baseline – Serum Chemistry (Safety Population)

Table 14.3.5.3 Clinical Laboratory Summary and Change from Baseline – Hematology (Safety Population)

Table 14.3.5.4 Clinical Laboratory Shift from Baseline – Hematology (Safety Population)

Table 14.3.5.5 Clinical Laboratory Summary and Change from Baseline – Coagulation and Platelet Count (Safety Population)

Table 14.3.5.6 Vital Sign Summary and Change from Baseline (Safety Population)

Table 14.3.5.7 Summarization of Weight (Safety Population)

Table 14.3.5.8 12-Lead Electrocardiogram Summary and Change from Baseline (Safety Population)

Table 14.3.5.9 Summarization of Bleeding Time (Safety Population)

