Appendix 16.2.8.4 Vascular Access Site Reaction Assessment (Safety Population)

Subject Number	Cohort/ Treatment	Study Day	Study Hour	Collection Date	Actual Time	Was a Reaction Observed?	If yes, Grade (1,2 or 3)
X	1/A	1	Predose	DDMMYYYY	HH:MM	XXX	X
			4 Hours postdose	DDMMYYYY	HH:MM	XXX	X
		3	Start of HD	DDMMYYYY	HH:MM	XX	
			20 min Post HD	DDMMYYYY	HH:MM	XXX	X

Note: Treatment: A = 0.5 µg/kg bolus dose of E-WE Thrombin followed by a 0.25 µg/kg/hour continuous infusion over 4 hours for a total dose of 1.5 µg/kg

B = 1.0 µg/kg bolus dose of E-WE Thrombin followed by a 0.5 µg/kg/hour continuous infusion over 4 hours for a total dose of 3.0 µg/kg

P = Placebo

HD = Hemodialysis

Program: /AXXXXX/ECR/sas_prg/stsas/lis_PROGRAMNAME.sas DDMMYYYY HH:MM

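### The by-treatment, by-time-point summary of vascular access site reactions committed to in Protocol 14.3.1 has no table in the SAP, and SAP Section 8 does not declare the omission

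*SAP*

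**What the plan says.** **Primary outcome.** Protocol 9.2 and SAP 2.2 name access site reactions within the number and severity of adverse events. Both say safety is evaluated against pre-treatment as well as placebo.

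**Protocol analysis commitment.** Section 14.3.1 states: "Safety data including ECGs, vital signs assessments, clinical laboratory results, and vascular access site reaction will be summarized by treatment". The sentence goes on to specify the two active doses and pooled placebo, and a breakdown by collection time.

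**SAP handling.** Section 7.10 sets four assessment times: Day 1 predose, Day 1 at 4 hours, Day 3 at the start of HD, and Day 3 at 20 minutes after HD. New abnormal findings that do not fit past skin injury are reported and summarised as adverse events. For the rest, "All data collected on the CRF will be listed". The display is Appendix 16.2.8.4, a listing with a yes/no reaction field and a grade column headed "If yes, Grade (1,2 or 3".

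**SAP tables.** The 14.3.5 list in Section 9.2 ends at "Table 14.3.5.9 Summarization of Bleeding Time (Safety Population" and has no access site reaction entry. Under SAP 7.3, only treatment-emergent events are summarised, in Tables 14.3.1.1 to 14.3.1.3.

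**Declared changes.** SAP Section 8 reads: "The analyses described in this SAP are aligned with those analyses described in the protocol".

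**The concern.** Four kinds of safety data share one sentence of the protocol and one promised display. Three of them received tables in the SAP. The fourth is the only adverse-event type that the primary outcome mentions by name, and its structured assessment received a listing. A reader of the study report would have to count by hand from that listing to learn how many patients per group had a reaction at each visit, or how many had one before dosing.

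The predose record matters in this population. Patients on chronic HD can carry existing access site findings into the study, so a post-dose finding is hard to read without the patient's predose state and the placebo group's course beside it. The protocol planned for that comparison.

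The Section 8 statement adds to the problem. Someone relying on it would not know that a planned safety summary had been left out.

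**Working it through.** The plan states no figure to reproduce. The sample size "The sample size chosen for this study was selected without statistical considerations", so no power or error-rate calculation depends on this point. The check is a comparison of text, followed by a count.

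**Step 1. Items in the Protocol 14.3.1 sentence against the SAP table list.**

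| Item | SAP summary table |
|---|---|
| ECGs | 14.3.5.8 |
| Vital signs | 14.3.5.6 |
| Laboratory results | 14.3.5.1 to 14.3.5.5 (chemistry, haematology, coagulation and platelets; SAP 7.4 keeps urinalysis to listings) |
| Access site reaction | None; listing 16.2.8.4 only |

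**Step 2. Where each kind of finding ends up.**

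| Finding | Adverse-event tables | Listing 16.2.8.4 | Table by scheduled time |
|---|---|---|---|
| Present at Day 1 predose | No, because it is not treatment-emergent (unless it is reported as worsening after dosing) | Yes | None |
| Post-dose, new and reported as an adverse event | Yes, by System Organ Class and Preferred Term, treatment, and severity Grades 1 to 4 | Yes | None |
| Post-dose, attributed to past skin injury | No | Yes, if recorded as a reaction | None |

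The last column is empty throughout, and two of the three rows reach no summary of any kind. Whether a post-dose finding is summarised depends on the judgement that it is new.

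**Step 3. Size of the missing display.** Protocol 14.1 gives "36 patients in total (18 per cohort with a ratio of 2:1 of active study drug:matching placebo".

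- Groups: 12 on 1.5 µg/kg, 12 on 3.0 µg/kg, and 6 + 6 = 12 on pooled placebo.
- Cells promised: 3 groups × 4 times = 12. SAP tables with that layout: 0.
- Assessments if all patients complete all four times: 36 × 4 = 144 yes/no answers. A grade is recorded only when the answer is yes, so 144 is an upper limit on assessments and not a count of graded reactions.
- Predose assessments: 36 × 1 = 36, or 36/144 = 25%. None reaches a table as a predose value.
- Post-dose assessments: 36 × 3 = 108. These contribute to a table only through an adverse event report.

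The documents give no expected reaction rate, so the number of reactions affected cannot be estimated.

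**The case against.** The strongest reply is that the primary outcome is still served. Protocol 9.2 places these reactions within the number and severity of adverse events, and the SAP sends new abnormal findings to exactly those tables. SAP 7.3 counts events that begin or worsen from dosing onwards, so new or worsened reactions reported as adverse events are shown by arm. This stands. It answers three inferences a reader might draw:

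- **That the SAP does nothing but list reactions.** The sentence in 7.10 just before the listing statement says otherwise.
- **That there is no comparison with placebo by grade.** Table 14.3.1.3 gives treatment-emergent counts by Preferred Term, treatment and Grades 1 to 4. It lacks an any-reaction row and time points.
- **That spreading reactions over several Preferred Terms would conceal them.** The documents show no coding, and Table 14.3.1.1 also has System Organ Class rows in which each patient counts once.

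A reader might also take the Grade 1 to 3 field for an SAP error, because Protocol 13.2.8.3 describes a 4-point scale. The field follows the local-reaction table in Protocol 13.2.5, which defines only three grades. At most, those two protocol sections need reconciling.

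Nor is this a gap in bleeding data. The graded reactions are pain, tenderness, erythema and induration; bleeding time is separate and has Table 14.3.5.9.

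Finally, Protocol 14.3 lets the SAP modify the planned analyses, requiring only that "any major modifications of the primary endpoints definition and/or its analysis will also be reflected in a protocol amendment". The documents do not define major, and omitting one descriptive table does not clearly qualify, so they do not establish that an amendment was needed. Permission to modify does not make the Section 8 statement correct, however.

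**Conclusion.** The point holds as a departure in planned reporting that should be corrected. The protocol commits to a summary by treatment and collection time; the SAP has none and says it is aligned. New abnormal findings are still summarised by treatment and severity as treatment-emergent events. What is lost is the any-reaction comparison at the four scheduled times, all predose findings, and findings attributed to past skin injury. For this component, the evaluation against pre-treatment and placebo is therefore not delivered by scheduled time.

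The effect is limited to descriptive reporting: 12 group-by-time cells from at most 144 assessments. It alters no test, estimate or sample size, and the individual records will still be listed. The counts assume the planned 36 patients and complete attendance. The conclusion also takes the SAP's table list as complete. SAP Section 10 says the shells may change and may not reflect every aspect of the study, but neither 7.10 nor the table list suggests that this table was intended.

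**What to change.** Add one table to the 14.3.5 series, Safety Population, with columns for 1.5 µg/kg, 3.0 µg/kg and pooled placebo, showing:

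1. The number and percentage of patients with any access site reaction at each of the four scheduled times, with the number assessed as denominator.
2. The same by recorded grade, using Grades 1 to 3 as defined in Protocol 13.2.5.
3. A row for patients with a new or worsened reaction from Day 1 predose to Day 1 after HD: no reaction at predose and one afterwards, or a higher grade afterwards.

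Amend SAP 7.10 to refer to this table and correct Section 8. If the sponsor prefers not to add it, Section 8 should declare the departure from Protocol 14.3.1 and justify it. Do not add a Grade 4 to Appendix 16.2.8.4, because Protocol 13.2.5 defines none; any clarification of the three-grade and 4-point scales belongs in the protocol.

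The cost is one table from fields already planned for the listing, plus a few sentences of SAP text. No new data collection is needed.

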7.11 Bleeding Time

The time to clot (bleeding time) will be recorded following hemodialysis after the needle is removed from the vascular access site on Days -7, -5, -2, 1, and 3. Summary statistics will be calculated for time to clot by treatment and assessment timepoint.

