9.2 Study Endpoints

Primary outcome measures:

- The safety and tolerability of E-WE thrombin following active treatment will be evaluated versus pre-treatment and placebo by number and severity of AEs (including HD vascular access site reactions), physical examinations, bleeding time from the HD vascular access sites, vital sign measurements, 12-lead ECGs, clinical laboratory tests, and coagulation tests.

Secondary outcome measures:

- PD of E-WE thrombin will be measured by APC-PCI and plasma APC-PCI will act as a surrogate marker for E-WE thrombin drug exposure.
- Efficacy of antithrombotic activity will be evaluated by thrombus accumulation within the dialyzer cartridge (evaluated by visual inspection) after E-WE thrombin active treatment versus pre-treatment and placebo.
- Efficiency of HD will be assessed using BUN levels before and after dialysis to determine urea removed by 4 hours of dialysis (Kt/V and URR) after E-WE thrombin active treatment versus pre-treatment and placebo.

Other outcome measures:

- Development of antibodies to E-WE thrombin or WT thrombin after drug exposure.

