2.2 Endpoints

Primary outcome measures:

- The safety and tolerability of E-WE thrombin following administration of the active treatment will be evaluated versus pre-treatment and placebo by number and severity of AEs (including HD vascular access site reactions), physical examinations, bleeding time from the HD vascular access sites, vital sign measurements, 12-lead ECGs, clinical laboratory tests, and coagulation tests.

Secondary outcome measures:

- Pharmacodynamics of E-WE thrombin will be measured by APC-PCI and plasma APC-PCI will act as a surrogate marker for E-WE thrombin drug exposure.
- Efficacy of antithrombotic activity will be evaluated by thrombus accumulation within the dialyzer cartridge (evaluated by visual inspection) after E-WE thrombin active treatment versus pre-treatment and placebo.
- Efficiency of HD will be assessed using BUN levels before and after dialysis to determine urea removed by 4 hours of dialysis (Kt/V and URR) after E-WE thrombin active treatment versus pre-treatment and placebo.

Other outcome measures:

- Development of antibodies to E-WE thrombin or WT thrombin after drug exposure.

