7.5 Vital Signs

Vital signs tests (HR, BP, RR and T) will be assessed at Screening, Day -8 check-in, within one hour prior to start of HD on Days -7, -5, -2, 1 and 3 and 1 hour postdose on Day 1.

Vital sign results will be summarized by treatment and time point. Change from baseline will be summarized in a similar way. Baseline is defined as the result closest and prior to the dose on Day 1, which may include unscheduled results, whichever is later. Postdose unscheduled events will not be included in summaries.

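### The SAP does not tabulate the incidence of access-site bleeding that Protocol 14.3.1 plans, and SAP section 8 does not declare the omission

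*SAP*

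**What the plan says.** Protocol 9.2 makes access-site bleeding time one of the primary outcome measures, under the sentence that begins "The safety and tolerability of E-WE thrombin following active treatment will be evaluated versus pre-treatment and placebo by number and severity of AEs". SAP 2.2 repeats the list: "evaluated versus pre-treatment and placebo by number and severity of AEs (including HD vascular access site reactions), physical examinations, bleeding time".

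Protocol 14.3.1 sets out the analysis. It names two measures, "Incidence and time of bleeding from the HD access sites on the AV fistula (or AV graft", to be counted and recorded, and then states: "Active treatment versus pre-treatment, placebo, and post-treatment results will be compared". For quantitative safety data in general it adds: "Descriptive statistics using appropriate summary statistics will be calculated for quantitative safety data as well as for the difference to baseline, when appropriate".

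SAP 7.11 plans one thing for bleeding: "Summary statistics will be calculated for time to clot by treatment and assessment timepoint". The only bleeding summary in the SAP's table list is Table 14.3.5.9. Its shell shows n, mean, SD, minimum, median and maximum for Days -7, -5, -2, 1 and 3 under the two doses and pooled placebo. A programmer note says that the value analysed is the length of time pressure was held on the puncture site, taken from item #4 of the Dialyzer Assessment CRF page.

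SAP section 8 states: "The analyses described in this SAP are aligned with those analyses described in the protocol".

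**The concern.** The protocol plans two bleeding measures and the SAP analyses one. Incidence does not appear in SAP 7.11, in the list of Section 14 tables or in the shell, and the section reserved for departures from the protocol reports none. Someone who relies on section 8 would not know that a planned piece of the safety analysis had gone.

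There is also no defined baseline and no within-patient change for bleeding time. Protocol 8.3.1 includes the heparin-free pre-dose period to establish a baseline, and bleeding time is measured at three sessions in it. A table of arm statistics by day cannot say how many patients bled longer on Day 1 than in their own pre-dose session. For an antithrombotic whose hemostatic safety in this population is described as not yet known (Protocol 8.4), that is a natural question.

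**Working it through.** **Reproducing a stated figure.** None exists. The protocol says that the sample size was chosen without statistical considerations, and no effect size, SD or error rate is given for bleeding time. The check is therefore a comparison of text.

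**Planned against delivered.**

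| Element | Protocol | SAP |
|---|---|---|
| Time of bleeding | 9.2 and 14.3.1 | 7.11 and Table 14.3.5.9, all arms and days |
| Incidence of bleeding | 14.3.1, not defined | Absent from 7.11, the table list and the shell |
| Comparison with placebo and with other days | 14.3.1 | Arms and days side by side; no contrast calculated |
| Difference to baseline | 14.3.1, only where appropriate | Not given for bleeding time |
| Departure declared | – | None in section 8 |

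**Does another output supply incidence?**
- Access-site reactions are summarised as AEs (SAP 7.10), but only treatment-emergent AEs are tabulated (SAP 7.3), so pre-dose events drop out. The reaction assessment itself covers only Days 1 and 3.
- Appendix 16.2.5.9.2 lists time to hemostasis by patient and day. Incidence could be derived from it, but a listing is neither a count nor a comparison.

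**How the SAP treats other safety data.** Baseline and change are defined for chemistry and hematology (7.4), ECG (7.7) and vital signs, where "Change from baseline will be summarized in a similar way". Coagulation tests and platelets on dialysis days get a same-session fold change. Weight (7.6) is summarised by time point only and urinalysis is only listed. Bleeding time is not the sole variable without a change from baseline.

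**Form of the data.** Protocol 13.2.6 checks first after 10 minutes of pressure and then every 5 minutes. If the CRF follows this, recorded values are 10, 15, 20 and so on, and 10 means 10 or less. A count by category suits such values, and the proportion above 10 minutes is those still bleeding at the first check. The CRF is not in the documents, so this is conditional.

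**Illustration of the categories (all true times assumed).** Let T be lognormal with log-SD 0.4. The recorded value is 10 if T ≤ 10, otherwise 10 + 5 × ceil((T − 10)/5). Its mean is 10 + 5 × Σ P(T > 10 + 5k) over k ≥ 0. Before and after an assumed 50% rise:

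| True median (min) | Recorded median | Mean | SD | Share above 10 min |
|---|---|---|---|---|
| 5 | 10 → 10 | 10.2 → 11.4 | 1.1 → 2.9 | 4% → 24% |
| 7 | 10 → 15 | 11.1 → 14.0 | 2.5 → 4.7 | 19% → 55% |
| 9 | 10 → 15 | 12.6 → 17.2 | 3.8 → 6.2 | 40% → 77% |
| 12 | 15 → 20 | 15.6 → 22.0 | 5.5 → 8.2 | 68% → 93% |

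The planned mean and SD move in every row. What the count adds is how many patients are involved.

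**Choice of baseline.** Simulated patients, assumed true median 7, between- and within-patient log-SD 0.35 and 0.25, Day 1 against two possible baselines:

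| Baseline | No effect: longer / shorter | 50% rise: longer / shorter |
|---|---|---|
| Median of the three pre-dose values | about 12% / 8% | 48% / 1% |
| Last pre-dose value | about 11% / 11% | 46% / 3% |

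The last value is balanced when nothing has happened. The median of three leans towards apparent prolongation.

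**Precision.** Exact 95% intervals for an incidence in an arm of 12: 0/12 gives 0 to 26.5%; 1/12 gives 0.2 to 38.5%; 3/12 gives 5.5 to 57.2%.

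**The case against.** The strongest reply is that little is lost. The primary outcome list names bleeding time, and the SAP summarises that on every dialysis day for both doses and pooled placebo, so pre-treatment, placebo and post-treatment results stand next to each other. Incidence is mentioned only in Protocol 14.3.1, without a definition and without a specified table. Protocol 14.3 allows the SAP to modify the protocol's plans. With 36 patients, own-control comparisons and counts above 10 minutes can be read from the listing.

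Most of this stands and limits the point. It does not supply a summarised incidence, and permission to modify a plan does not make section 8's statement of alignment correct.

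Three stronger readings are tempting, and the documents do not support them:

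- *The protocol requires a within-patient comparison.* It says that results will be compared, and it plans difference to baseline only where appropriate. The rule allowing an average of predose values as baseline is in the pharmacodynamic section (14.3.3). No passage asks for a paired count of bleeding times.
- *The SAP drops the primary outcome analysis.* It does not: bleeding time is tabulated in full.
- *The 10-minute floor hides prolonged bleeding.* That depends on true times which the documents do not give. Of the cases shown, only the lowest assumed median leaves the recorded median at 10 after a 50% rise, and even there the mean and SD increase.

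**Conclusion.** The point holds in a limited form. Protocol 14.3.1 plans an incidence of access-site bleeding; the SAP neither defines nor tabulates it, and section 8 does not say so. That rests on the text alone. The missing within-patient comparison is a worthwhile and cheap addition, but its absence is not a breach of the protocol.

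Severity is minor to moderate: worth correcting before the SAP is applied, with no effect on design or data collection, and the underlying values remain recoverable from the listing. The size of the omission cannot be expressed as a number. The figures above illustrate what a count would show under assumed bleeding times; they do not measure the defect. With 12 patients per active arm, an added incidence can only be descriptive.

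**What to change.** In SAP 7.11 and Table 14.3.5.9 keep the planned statistics and add:

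1. n (%) of patients by treatment and day with length of pressure 10 or less, >10–15, >15–20 and >20 minutes. State that the proportion above 10 minutes is the SAP's working definition of the incidence that the protocol leaves undefined, provided the CRF follows the checks in Protocol 13.2.6. If more than one puncture site is recorded in a session, use the longest time.
2. Change from baseline, with baseline the last pre-dose session (normally Day -2), in line with the closest-before-dose rule in SAP 7.4 and 7.5. Report n (%) longer, the same or shorter on Day 1 and on Day 3, by dose and pooled placebo, labelled descriptive.
3. If the CRF follows Protocol 13.2.6, a footnote that 10 minutes means 10 or less.

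Confirm that the time to hemostasis in Appendix 16.2.5.9.2 is the CRF item #4 value, and use one name for it. If incidence is not added, record the departure in SAP section 8.

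Cost: one SAP paragraph and one revised table. No new data are needed and the pressure procedure is unchanged.
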